GlobalSurg (<http://globalsurg.org/>) is a collaboration between practising surgeons from around the world, performing research in surgery to foster local, national and international research networks. The collaborative model used has previously been described elsewhere [13] and has already facilitated three multicentre, international, prospective cohort studies including a total of 46,186 patients undergoing emergency and elective abdominal surgery [14-16]. The NIHR Unit on Global Surgery was established in 2017 and is a consortium between the Universities of Birmingham, Edinburgh and Warwick, together with international partners. The unit's objective is to advance the education of medical students and doctors in surgical science, clinical research and audit methods by promoting participation in collaborative clinical research and audit studies.

STUDY SETTING

The study is open to any hospital worldwide that performs emergency and/or elective cholecystectomy. An eligible hospital must collect consecutive patients undergoing cholecystectomy during the specified study period, following appropriate registration of the study according to local hospital regulations.

Included centres should ensure data collection is >90% complete. Centres with >10% missing data, when including all data points, will be excluded from the final analysis and removed from the authorship.

There is no minimum number of patients per centre, as long as all eligible patients treated during the study period are included.

STUDY POPULATION

Summary

The study population includes consecutive patients, admitted to hospital within the pre-specified data collection periods, undergoing cholecystectomy as the index operation.

Inclusion Criteria

- **Age:** All adult patients (greater than or including 18 years of age).
- **Procedure:** Primary cholecystectomy, where this is the main procedure planned.
- **Approach:** Open, laparoscopic (standard and single-port), and robotic. Gasless laparoscopic and robotic approaches are included. Laparoscopic and robot converted cases are also eligible.
- **Urgency:** Elective, delayed and emergency procedures.

Exclusion Criteria

- **Procedure:** Patients having a cholecystectomy as a part of another surgical procedure; for example, Whipple's procedure, bariatric, anti-reflux, or transplant operations, should be excluded.
- **Indication:** Patients with Mirizzi syndrome should be excluded.

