1. **30-day follow-up:** should be performed for all recruited patients. Each patient will be followed-up for 30 days starting on the day of surgery (day 0).
2. **One-year follow-up:** due to the nature of the study, aiming to assess bile duct injury and unsuspected gallbladder cancers, we aim to collect one-year follow-up data on all recruited patients. Each patient will be followed-up for one year starting on the day of surgery (day 0). Patients are excluded from one-year follow-up if they had died within 30 days of index surgery, as there would be no additional data to collect from these patients since the 30-day follow-up that had already been completed previously. Additional collaborators can be recruited to aid one-year follow-up data collection once the follow-up period begins (31st Jul 2024).

Local arrangements for successful 30-day and one-year follow-up may include: reviewing patient notes, reviewing patient status in outpatient clinics or via telephone interview at 30 days (if this is normal practice) and checking for readmission through handover lists. Follow-up should be performed in line with current routine practices of each hospital. No additional telephone, in-person or questionnaire-based follow-up is required. Source data may be acquired from hospital in-patient notes, clinical electronic systems, or outpatient letters.

Key to successful 1-year follow-up:

1. *Ensure you keep a list of all patient ID and corresponding RedCap ID in a safe, secure computer to allow follow-up of these patients. This will be in the form of an encrypted spreadsheet held securely on the local hospital computer network by a member of the data collection team (a hospital lead, supervising consultant/attending, or audit officer).*
2. *Where it is anticipated that a hospital lead will rotate to another hospital, then the supervising consultant should facilitate the secure storage of patient ID and corresponding RedCap ID.*
3. *Ensure the audit office / local governing bodies are clear this will be a follow-up study.*
4. *In high-volume centres where achieving high data completeness may be burdensome, involvement additional team members to provide support can be permitted.*

Table 1: Data collection periods

Dates	Description
00:00 31 st July – 23:59 13 th Aug 2023	Start of data collection period 1 (+ 30-day follow-up: ends 12 th Sep 2023) (+ one-year follow-up: ends 13 th Aug 2024)

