Validation by primary data collection teams:

- Follow-up methodology at patient level: all hospitals will self-report the methods used to determine 30-day outcomes.
- Patient identification methodology: all hospitals will self-report the methods used to identify patients who fulfil the inclusion criteria.

Validation by independent teams:

- Case ascertainment: hospital records will be reviewed to identify patients fulfilling the inclusion criteria within a 2-week data collection period and comparing this to the actual number of cases submitted. This will be performed by individuals not involved in collecting the primary data. By comparing samples, a quantitative estimate of case ascertainment will be produced by the central data team.
- Data accuracy: a subset of collected variables will be validated by individuals who are independent of the primary data collection process. Following the “case ascertainment” stage, validators will be asked to provide data for a subset of variables, two patient variables, two operation variables, and two outcome measures.

Project Team Structure

Each registered centre must have a supervising consultant/attending to ensure adequate data quality. In the case that the hospital lead is a registrar/resident then they must recruit a consultant/attending to supervise the study. The hospital lead should also ensure that they recruit independent data validators (registrars/residents or consultants/attendings) to perform the data validation outlined in the section above.

For data collection, the hospital lead should recruit a “mini-team” of up to five local collaborators for each data collection period (**Table 1; page 15**). Medical students, doctors (non registrars/residents or consultants/attendings) and nurses can act as local collaborators and their participation is encouraged. The same “mini-team” can cover different time periods at each hospital if they wish to. Each team should include at least one qualified doctor to provide additional local support for participating medical students or nurses. Additional collaborators can be recruited to aid one-year follow-up data collection once the follow-up period begins (31st Jul 2024). A detailed specification of each role can be found below (see **pages 23-24**).

STATISTICAL CONSIDERATIONS

Primary Outcome Measure

The primary endpoint of this study is the compliance to pre-, intra-, and post-operative audit standards (see pages 9-10).

Secondary Outcome Measures

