The secondary endpoints include:

- Rates of achieving a critical view of safety.
- Rates of different bailout procedures initiated when safe cholecystectomy is compromised.
- 30-day and one-year rates of textbook outcomes [2] for cholecystectomy, which covers: postoperative complications (Clavien-Dindo classification), intraoperative complications (including bile duct and vascular injuries), length of stay, readmission, mortality, and postoperative imaging or intervention.
- Unsuspected gallbladder cancer rates and their 30-day and one-year outcome rates, which includes: (1) complication rates (Clavien-Dindo classification); (2) time-to-recurrence rates (time from surgery to recurrence); and (2) revisional surgery rates (liver resection, bile duct resection and/or lymph node dissection).
- A description of the global variation in the availability of cholecystectomy services, training and sustainable practice.

Control of Bias and Confounding

Data will be collected on audit standards and confounding factors for risk-adjusted analyses. These include age, sex, body mass index, American Society of Anaesthesiologists (ASA) grade, and relevant comorbidities. Variables including operative urgency, operative contamination, and operative approach will also be collected. Without appropriately adjusting for risk factors, it is likely that any findings would be biased and unable to be appropriately analysed on an international scale. A full list of required data fields is available in **Appendix B**, and on the REDCap database.

Data Analysis & Sample Size

Variation across different international health settings will be tested using the human development index (HDI) countries [17] a composite statistic of life expectancy, education and income indices published by the United Nations. Initially, data will be reported using descriptive analyses. Comparisons between groups will be undertaken using appropriate parametric and non-parametric analyses. Multilevel logistic regression multivariate models will be constructed to account for case mix, with population stratification by hospital and country as random effects.

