- All **GECKO** data will be collected and stored online through a secure server running the Research Electronic Data Capture (REDCap) web application. REDCap allows collaborators to enter and store data in a secure system. Collaborators will be given secure REDCap project server login details, allowing secure data storage on the REDCap database.

All data should be handled in accordance with national and local data governance policies. For instance, collaborators in the UK should seek their trust's Caldicott Guardian's permission to submit data to the REDCap system. **No data should be uploaded to REDCap prior to written approval from the Caldicott Guardian or ethical board.** No patient identifiable information should be uploaded or stored on the REDCap database without explicit permission from the trust's Caldicott Guardian. In other countries, no data should be uploaded to REDCap without local governance authorisation.

AUTHORSHIP

All authors will be credited in accordance with National Research Collaborative Authorship guidelines, and research outputs from **GECKO** will be listed under a single corporate authorship of GlobalSurg Collaborative, NIHR Global Surgery Unit [16,19,20].

Requirements for authorship on **GECKO** outputs include:

- Successful in obtaining all relevant local approvals for conduct of the **GECKO** study.
- Have completed the site survey.
- Successful data collection of at least one eligible patient per period for each site.
- Individual sites must also ensure:
 - A complete data set (>95% data points entered per record).
 - High case ascertainment (>90%, [see pages 16-17](#)).
 - All data has been uploaded by the specified database closure deadline.

All collaborators will be listed as PubMed-citable collaborators in accordance with the roles defined below (so long as the minimum requirements for authorship are met):

- **Writing Group:** A group of medical students, doctors and external advisory board members responsible for the overall scientific content, data analysis, and preparation of research manuscripts.
- **Steering Committee:** A core group of medical students and doctors who have overall responsibility for protocol design, project co-ordination, and data handling.
- **External Advisory Group:** A panel of international, cross-disciplinary field experts who are able to ensure contextual and scientific relevance of the protocol design, data fields and data interpretation.

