Discussed at MDT	 Yes  No	Adjuvant treatment  Chemotherapy  Radiotherapy  None	
Revisional surgery	 Yes  No - not required  No - unresectable tumour		
Type of revisional surgery (Tick all that apply)	 Liver resection (Extent:  Liver bed  1 segment  2 segments  ≥ 3 segments)  Bile duct resection  Lymph node dissection	Days from histology result to revisional surgery --	If revisional surgery
Pathology results	Resection margin status:  R0  R1  R2 Lymphovascular invasion:  Yes  No Perineural invasion:  Yes  No		
Recurrence on imaging at one year	 Yes (Days from surgery to recurrence: __)  No		
Section 6: One-year outcomes			
Highest one-year Clavien-Dindo (CD)	 0  I  II  IIIa (Radiological drainage?  Yes  No)  IIIb (Re-operation?  Yes  No)  IVa  IVb  V (Postop day of death: __)	Total number of readmissions --	

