APPENDIX B: DATA DICTIONARY

Pre-operative Data Fields	Required data (definition / comment)
1. Patient age	Years (Whole years at the time of operation)
2. Patient sex at birth	Male / Female
3. ASA grade	I / II / III / IV / V (Appendix D for definitions)
4. Body Mass Index (BMI in kg/m ²)	Underweight BMI Below 18.5 / Normal weight BMI 18.5-24.9 / Pre-obesity BMI 25.0-29.9 / Obesity class I BMI 30.0-34.9 / Obesity class II BMI 35.0-39.9 / Obesity class III BMI 40+
5. Clinical Frailty Scale	1 / 2 / 3 / 4 / 5 / 6 / 7 / 8 / 9 (Appendix D for definitions)
6. Comorbidities (Select all that apply)	
Myocardial Infraction (MI) / Congestive Heart Failure (CHF) / Peripheral Vascular Disease (PVD) Cerebrovascular Accident (CVA) or Transient Ischaemic Attack (TIA) / Dementia / Chronic Obstructive Pulmonary Disease (COPD) / Connective Tissue Disease (CTD) Peptic Ulcer Disease (PUD) / Hemiplegia / Leukaemia / Lymphoma / Human Immunodeficiency Virus (HIV) or Acquired Immunodeficiency Syndrome (AIDS) / Hypertension / Inflammatory Bowel Disease (IBD) / Diabetes Mellitus (Type 1 or Type 2). If yes: Diet-Controlled / Medication (non-insulin) controlled / Insulin-controlled Solid Tumour. If yes: Localised / Metastatic Liver Disease. If yes: Mild / Moderate to Severe Chronic Kidney Disease (CKD). If yes: Stage I / II / IIIa / IIIb / IV / V None of the Above
 
Definitions:
 
 eGFR for CKD stages: I ≥ 90; II = 60-90; IIIa = 45-59; IIIb = 30-44; IV = 15-29; V <15 Definitions for Liver Disease: Mild defined as chronic hepatitis or cirrhosis without portal hypertension; Moderate defined as cirrhosis and portal hypertension but no variceal bleeding history; Severe defined as cirrhosis and portal hypertension with variceal bleeding history.
7. History of acute cholecystitis or cholangitis	Yes / No
8. Number of admissions with biliary symptoms in previous 12 months prior to surgery	Number of admissions excluding the current one
9. Preoperative imaging (Select all that apply)	Yes / Unknown / No (Not available / Not indicated / Patient declined) for each of the following: USS / CT / ERCP / MRCP / Endoscopic Ultrasound (EUS) / Hepatobiliary IminoDiacetic Acid (HIDA)

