3. TNM grade (AJCC 8th edition) (Appendix D for definition)	
T category: Tis / T1a (lamina propria) / T1b (muscularis) / T2a (peritoneal side) / T2b (hepatic side) / T3 / T4
 
N category: N0 / N1 (1-3 nodes) / N2 (>3 nodes)
 
M category: M0 / M1

4. Discussed at MDT	Yes / No
5. Adjuvant treatment	No / Chemotherapy / Radiotherapy
6. Revisional surgery completed	
Yes / No (not required) / No (unresectable tumour)
 
 • If yes, type of surgery (select all that apply): Liver resection (liver bed / one segment / two segments/ ≥ 3 segments) / bile duct resection / lymph node dissection • If yes, time from histology result to revisional surgery: Number of days (whole number)
7. Pathology results if revisional surgery	
Resection margin status: R0 / R1 / R2
 
Lymphovascular invasion: Yes / No
 
Perineural invasion: Yes / No
 
Resection margin definition: R0 = microscopically negative for residual tumor; R1 = microscopically margins still demonstrate the presence of tumor; R2 = macroscopically-visible disease remains post-surgery.

8. Recurrence on imaging at one year	
Yes / No
 
If yes, time from surgery to recurrence: number of days (whole number)

One-year Outcomes	Required data (definition / comment)
1. Highest one-year Clavien-Dindo (CD) Grade	
0 / I / II / IIIa / IIIb / IVa / IVb / V
 
If CD IIIa: Radiological drainage (yes / No)
 
If CD IV: Re-laparoscopy (yes / No)
 
If CD V (death): please indicate time from index cholecystectomy to death: number of days (whole number)

2. Readmissions	Total number of readmissions

3. One-year complications
(Select all that apply)

Surgical site infection (CD Grade* 0 / I / II / IIIa / IIIb / IVa / IVb / V)

Postoperative pulmonary complications (CD Grade* 0 / I / II / IIIa / IIIb / IVa / IVb / V)

Bile leak (CD Grade* 0 / I / II / IIIa / IIIb / IVa / IVb / V)

Biliary stricture (CD Grade* 0 / I / II / IIIa / IIIb / IVa / IVb / V)

Bleeding (CD Grade* 0 / I / II / IIIa / IIIb / IVa / IVb / V)

Intra-abdominal collection (CD Grade* 0 / I / II / IIIa / IIIb / IVa / IVb / V)

Acute pancreatitis (CD Grade* 0 / I / II / IIIa / IIIb / IVa / IVb / V)

*For all of the above, please indicate the Clavien-Dindo grade associated with that complication

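### The form does not record whether or when patients with unsuspected gallbladder cancer were imaged for recurrence, so recorded recurrence is only a lower bound and survivors without it have no censoring date

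*Protocol*

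**What the plan says.** Under Statistical Considerations, Secondary Outcome Measures, the protocol lists outcomes for unsuspected gallbladder cancer at 30 days and one year, among them "time-to-recurrence rates (time from surgery to recurrence". Analysing the outcomes of these cancers is secondary aim 3, and the Follow-up Period section gives them as one of two reasons for following patients to one year.

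The source field is "Recurrence on imaging at one year" (Appendix B, Histology data fields, item 8; Appendix A, Section 5). Both appendices allow Yes or No. After Yes, the case report form asks for "Days from surgery to recurrence". After No, nothing more is asked.

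One-year follow-up draws on routine care and existing records: "No additional telephone, in-person or questionnaire-based follow-up is required" (Follow-up Period). No surveillance scan is required. Under Data Validation, "all hospitals will self-report the methods used to determine 30-day outcomes"; one-year methods are not mentioned.

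For preoperative imaging the same dictionary is more detailed: "Yes / Unknown / No (Not available / Not indicated / Patient declined) for each of the following" (Appendix B, Pre-operative Data Fields, item 9).

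**The concern.** The outcome is defined by imaging, but whether imaging took place is not recorded. A patient scanned and found clear, and a patient never scanned after staging, can both be entered as No. This has three consequences.

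- The Yes share understates recurrence by an amount that the dataset cannot show.
- A time-to-event analysis needs a last date on which a patient was known to be free of recurrence. Survivors coded No have none, so an analyst would have to assume one, such as day 365.
- The study is about variation between health settings. If recurrence were compared between settings, one that images less could appear to have less recurrence.

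This cannot be left to a statistical analysis plan. Such a plan can choose an estimator or a censoring rule, but it cannot supply an imaging status that was never collected.

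**Working it through.** **Step 1: does any other field give imaging status?**

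| Field (Protocol) | What it shows | Why it does not answer the question |
|---|---|---|
| Unplanned re-imaging (Appendix B, 30-day Outcomes, item 3) | Imaging in the early postoperative period | Stops at 30 days |
| Staging investigations (Appendix B, Histology, item 2) | Modality, and days from the histology result | Initial staging, not later imaging for recurrence |
| Imaging available (Appendix C) | What the hospital has, on or off site | Not who was scanned |
| Self-reported follow-up methods (Data Validation) | How 30-day outcomes were found | Does not cover one year |
| One-year Clavien-Dindo grade V (Appendix B, One-year Outcomes, item 1) | Death, with its day | Dates deaths, but gives no last-imaging date for survivors |

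None does. Death can be handled and is not part of the point.

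**Step 2: how much could be hidden?** The protocol states no figure for this outcome, so there is none to reproduce. The rates below are assumptions. Let r be the true one-year share with recurrence that imaging would show, and q the chance that such a patient is imaged. If relapses that are not imaged are entered as No:

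recorded share = r × q

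| r | q = 100% | q = 90% | q = 60% | q = 30% |
|---|---|---|---|---|
| 20% | 20% | 18% | 12% | 6% |
| 30% | 30% | 27% | 18% | 9% |
| 40% | 40% | 36% | 24% | 12% |

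Nothing is lost if every relapse is imaged. Two settings with r = 30% but q of 90% and 30% would show 27% and 9%, although true recurrence is the same.

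**Step 3: is that large beside sampling error?** The protocol anticipates about 15000 patients. If 0.2% to 1% have unsuspected cancer (an assumption), that is 15000 × 0.002 = 30 to 15000 × 0.01 = 150 cases. The 95% Wilson interval around 30% is:

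- 9/30: 16.7% to 47.9%
- 45/150: 23.2% to 37.8%

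A recorded 18% lies inside the first interval and outside the second. With few cases the distortion is within chance; with many it is not.

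**Step 4: what would recording imaging status add?** Take 150 cases, of whom 90 were imaged and 27 had recurrence.

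- Among all cases: 27/150 = 18%
- Among those imaged: 27/90 = 30%
- If all 60 unimaged patients had relapsed: (27 + 60)/150 = 58%

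The present form gives only the 18%. Any of the 123 patients coded No might be unimaged, so its formal upper bound is (27 + 123)/150 = 100%. With imaging status recorded, the range is 18% to 58%.

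**The case against.** The strongest reply is that this is a routine-data study and the field means what it says: No is read as no recurrence recorded on imaging in the notes. That is right as far as it goes. A reader might infer that a No carries no information, but the documents do not support that. The Yes share remains usable as a lower bound. What a No does not show is that the patient was free of recurrence.

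A reader might also infer that the missing status is lost for good. It is absent from the dataset as collected. However, sites keep a list linking patient and REDCap identifiers (Follow-up Period), and could be asked again before the record identifier is stripped (Data Governance). The protocol plans no such step.

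A third tempting inference is that the completeness rules push sites to enter No. The rules are "Centres with >10% missing data, when including all data points, will be excluded from the final analysis" (Study Setting) and, for authorship, "A complete data set (>95% data points entered per record" (Authorship). Counting the numbered items in Appendix B, a malignant record without bile duct injury has 15 + 16 + 6 + 1 + 8 + 3 = 49. One blank leaves 48/49 = 98%, above the per-record limit, and it hardly moves a centre-wide figure. The protocol also does not tell sites to code unimaged patients as No, so some may leave the item blank. The r × q arithmetic assumes that they enter No.

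The comparison by human development index is a general statement under Data Analysis & Sample Size and is not tied to this outcome, so that harm is conditional. Staging dates and the site survey would let analysts describe imaging access in outline, though not who was later scanned. The subgroup is small and the primary endpoint is untouched. These replies limit the reach of the point; they do not supply the missing field.

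**Conclusion.** The point holds as a gap in data capture. For unsuspected gallbladder cancer, the form does not record whether or when a patient was imaged for recurrence. Recorded recurrence is a lower bound of unknown tightness, survivors coded No cannot be censored at a known date, and a comparison between settings would mix recurrence with access to imaging. That no field supplies this status follows from the two appendices and needs no assumption.

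The size is not established. The cancer incidence, relapse rate and imaging rate used above are all assumed, and the loss is zero if every relapse is imaged. The documents do not show that a comparison across development groups of this outcome is planned, so no bias in such a result can be claimed. The point is worth acting on because the remedy is cheap, but it concerns one component of one secondary outcome in a rare subgroup.

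**What to change.** For malignant cases only, add one item to the histology section of the case report form and dictionary:

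*Imaged for recurrence within one year: Yes (days from index cholecystectomy to last imaging) / No (not available, not indicated, patient declined, died before imaging) / Unknown.*

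Open the recurrence item only after Yes. In the analysis:

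- report the number imaged beside every recurrence figure;
- censor patients without recurrence at last imaging;
- give recurrence among those imaged and among all cases, with the upper bound if every unimaged patient had relapsed;
- do not compare development-index groups without the share imaged in each.

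If one-year forms have already been completed, the same question could be put to sites through their local lists before record identifiers are removed.

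The cost is one conditional item on about 30 to 150 records under the assumed incidence, filled from the same notes without patient contact. It has two limits. It does not find relapses in patients who were never imaged, and where imaging is prompted by symptoms the rate among those imaged will be too high. Both figures should therefore be reported together.

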Further prespecified subgroup analyses will be made by operative approach (open, laparoscopic and converted), and operative urgency (elective, emergency and delayed surgery). Audit standards (see pages 9-10) and site survey (Appendix C) will guide exploratory analysis into the global variation in the provision of cholecystectomy and available resources. However, it is acknowledged that some audit standards are designed for high-income settings and therefore their attainment will not be considered mandatory or a potential definitive measure of quality in global cholecystectomy.

Identification of hospital or surgeon-specific performance will not be reported. Following analysis, results will be fed back to participants at the centre level, but no other centres will be identifiable.

Based on previous GlobalSurg studies [14-16], GECKO is anticipated to include around 500 centres globally. With consideration to recent figures provided by previous collaborative studies [3,5] on cholecystectomy, a sample of approximately 15000 patients is anticipated. The recent multi-society practice guidelines on prevention of bile duct injury [8] advised that a study adequately powered to detect and report on bile duct injury would require at least 9000 patients.

DATA GOVERNANCE

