2. Intraoperative antibiotics*	
Yes (Prophylactic / Intraoperative spillage / Cholecystitis) / No *Defined as administration of antibiotics at least 30 minutes prior to skin incision to end of operation

3. Primary operator	
Consultant or attending Senior trainee (i.e., senior registrar or resident with >4 years surgical training/residency) Junior trainee (i.e., junior registrar or resident with ≤ 4 years surgical training/residency) Non-surgeon (e.g., medical practitioner or nurse)
 
If Consultant: What specialty? (General / Oesophago-gastric (OG) / HPB / Colorectal / Breast / Vascular / Other) If Trainee: Was this a training operation? (Yes / No). Was a consultant present? (Yes / No) If any: Number of cholecystectomies performed prior to this procedure: 0-50 / 51-100 / 101-200 / >200

4. Operative approach	
Open / Open conversion / Laparoscopic (Standard / Single Incision Laparoscopic Surgery (SILS)) / Robotic (Standard / SILS)
 
 If open, why: No laparoscopic equipment / Surgeon not trained in laparoscopy / Laparoscopy equipment broken / Multiple previous surgery / Disease severity. If open conversion, why: Suboptimal view / Adhesions / Not able to safely dissect CVS / Suspected bile duct injury / Patient unable to tolerate pneumoperitoneum / Bleeding / Bowel injury / Laparoscopic or robotic equipment failure / Suspected or actual cholecystoduodenal or cholecystocolonic fistula. If laparoscopic or robotic: was this gasless (Yes / No), were reusable equipment used? (Yes / No).
5. Intra-operative difficulty score – this is for minimally invasive surgery	
I / II / III / IV / V (Nassar Grade: Appendix D for definitions)

6. Was the Critical View of Safety (CVS) obtained (all three) – this is for minimally invasive surgery	
Yes / No If no, which criteria was met: 1) Clearing fat and fibrous tissue from the hepatocystic triangle.

	2) The lower third of the gallbladder being cleared from the cystic plate. 3) Only two structures are attached to the gallbladder.
7. Was there a time-out to verify CVS	Yes / No Defined as a momentary pause that what one is seeing is likely the correct anatomy

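### The approach subgroups are formed partly by what happened in theatre, and completed robotic cases fall in none of them

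*Protocol*

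**What the plan says.** Protocol, Data Analysis & Sample Size, fixes three levels for the approach subgroup: "Further prespecified subgroup analyses will be made by operative approach (open, laparoscopic and converted".

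The Inclusion Criteria admit more than these three: "Open, laparoscopic (standard and single-port), and robotic", followed by "Laparoscopic and robot converted cases are also eligible". Appendix B, intra-operative field 4, records approach as "Open / Open conversion / Laparoscopic (Standard / Single Incision Laparoscopic Surgery (SILS)) / Robotic (Standard / SILS". Appendix A, Section 2, uses the same four categories. Conversion is one category, with a list of reasons and no entry for the approach that was abandoned. The reasons include "Not able to safely dissect CVS / Suspected bile duct injury / Patient unable to tolerate pneumoperitoneum / Bleeding / Bowel injury".

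Appendix B, intra-operative field 6, asks "Was the Critical View of Safety (CVS) obtained (all three" and limits the question to minimally invasive surgery. No instruction covers converted cases. Achieving the CVS is an intra-operative audit standard, so it is part of the primary endpoint, and its rate is also a secondary endpoint. The textbook outcome under Secondary Outcome Measures counts "intraoperative complications (including bile duct and vascular injuries".

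**The concern.** A subgroup should be defined by something fixed before the outcome starts to accrue. Conversion is a result of a minimally invasive attempt, and several of its recorded causes either are events the study counts or are closely tied to them. Once conversions are a separate level, the laparoscopic level means started and completed laparoscopically. Its results do not describe what happens to patients for whom laparoscopy is chosen.

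The levels also do not cover the eligible population. A robotic operation that is converted enters the converted subgroup, while one that is completed enters none. Robotic surgery is then visible in this analysis only through its failures.

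The form adds two gaps that no later analysis choice can close. Conversion rates cannot be split by laparoscopic or robotic start. And centres may differ on whether a converted case answers the CVS item, so the denominator of an audit standard may vary between sites for reasons unrelated to care.

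**Working it through.** The protocol states no figure that depends on these definitions, so there is none to reproduce. It gives no conversion rate, no event rate by approach and no robotic share. Those below are assumptions, used only to show the scale.

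**1. Coverage of the levels**

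- Eligible: open, laparoscopic, robotic, and conversions from either minimally invasive approach.
- Recorded: open, open conversion, laparoscopic, robotic.
- Analysed: open, laparoscopic, converted.

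Robotic is lost between the second and third lists. With the anticipated 15,000 patients and an assumed robotic share of 1% to 10%, that is 15,000 × 0.01 = 150 to 15,000 × 0.10 = 1,500 patients.

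**2. Overlap of conversion with endpoints**

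Failed CVS dissection corresponds to the CVS endpoint. Suspected bile duct injury, bleeding and bowel injury correspond to, or are closely tied to, the intra-operative part of the textbook outcome. Membership of the converted level therefore depends partly on the outcome.

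**3. Completed cases against started cases**

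Let c be the share of minimally invasive starts that are converted, p the event rate in completed cases and q the rate in converted cases. The rate in all starts is (1 − c)p + cq, and the completed-only rate falls short of it by c(q − p).

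- c = 2%, p = 5%, q = 15%: started 5.2%, shortfall 0.2 points (3.8% relative).
- c = 5%, p = 8%, q = 25%: started 8.85%, shortfall 0.85 points (9.6%).
- c = 10%, p = 8%, q = 25%: started 9.7%, shortfall 1.7 points (17.5%).
- c = 15%, p = 10%, q = 40%: started 14.5%, shortfall 4.5 points (31.0%).

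**4. Bile duct injury**

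Take the 0.4% elective figure in the audit standards as the rate in all minimally invasive starts. If a share s of injuries occurs in converted cases, the completed-only rate is 0.4% × (1 − s)/(1 − c).

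- c = 2%, s = 50%: 0.4% × 0.50/0.98 = 0.20%.
- c = 5%, s = 30%: 0.4% × 0.70/0.95 = 0.29%.
- c = 10%, s = 10%: 0.4% × 0.90/0.90 = 0.40%, no distortion, because converted cases then carry no excess.

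**5. CVS denominator, if converted cases skip the item**

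Assume CVS is achieved in 85% of completed and 20% of converted cases. Omitting converted cases overstates the rate by c(0.85 − 0.20) = 0.65c.

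- c = 2%: 83.7% becomes 85%, overstated by 1.3 points.
- c = 10%: 78.5% becomes 85%, overstated by 6.5 points.

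If every converted case answers, the overstatement is zero. Two sites with identical practice and 10% conversion would differ by the same 6.5 points if one answers for converted cases and the other does not. The bailout standard applies only when the CVS is not achieved, so an unanswered CVS item also makes its denominator unclear.

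**The case against.** The strongest defence is that the protocol is descriptive. It states no laparoscopic-versus-open effectiveness contrast, its aim is variation in audit compliance, and converted cases are displayed as their own group and not hidden among the open ones. The starting-approach grouping can be rebuilt from the existing field by adding laparoscopic, robotic and open conversion. That all stands. It means the planned table destroys no data, and a biased treatment comparison is not established. It does not make the laparoscopic row an intended-approach result, does not give robotic cases a place, and does not recover where a conversion began.

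On CVS, the defence is that a converted operation began minimally invasively and so can reasonably answer the item, and that failed dissection is still captured as a conversion reason. That is a fair reading, but so is the other one, because conversion is coded as a separate approach. A reader might infer that the CVS rate is biased upward. The documents support only that it would be if converted cases skip the item.

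A reader might also infer that the risk-adjusted models will condition on achieved approach and contamination, and so remove real differences between Human Development Index (HDI) groups. The text does not support this. In Control of Bias and Confounding, the factors named for risk adjustment are all pre-operative. Of the operative variables it says only: "Variables including operative urgency, operative contamination, and operative approach will also be collected". The protocol fixes no covariate set, and that detail commonly belongs in a SAP. Nor are the two variables purely consequences of care: the dirty contamination level exists before surgery, and the reasons for open surgery include disease severity and previous operations.

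**Conclusion.** The point holds for the subgroup definition and for the form. As fixed, the approach subgroups depend partly on intra-operative events, omit completed robotic cases, and rest on a form that records neither the origin of a conversion nor whether the CVS item applies to it.

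The expected direction is that the laparoscopic subgroup looks better than all minimally invasive starts, provided converted cases do worse. The size is not known. Across the assumed ranges the event rate is understated by 0.2 to 4.5 points (about 4% to 31% relative), and bile duct injury would read 0.20% to 0.40% against 0.4%. The CVS overstatement of 1.3 to 6.5 points carries the further condition that converted cases skip the item, and it uses one assumed pair of CVS rates. The urgency subgroup follows the admission pathway and is not affected. No conclusion is drawn about the risk-adjustment model.

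**What to change.** - Make starting approach the main approach subgroup: minimally invasive (laparoscopic, robotic, and converted from either) against planned open. Either give robotic its own level or state that it is merged with laparoscopic.
- Report conversion as an outcome of minimally invasive starts. Keep the table by achieved approach as a secondary description, labelled as such.
- Add one tick box under open conversion in Appendices A and B: converted from laparoscopic or from robotic.
- State at the CVS item that it is completed for every case started minimally invasively, including converted ones.

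The cost is a few lines of wording, one form field and one extra table. No further patients are needed. The main regrouping works with the approach field as it stands; only the origin of conversion and the CVS answers for converted cases depend on the change to the form.
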